11.2 Serious Adverse Experiences (SAE)

An SAE is defined as any AE occurring at any dose that results in any of the following outcomes:

- death
- a life-threatening adverse experience
- inpatient hospitalization or prolongation of existing hospitalization
- a persistent or significant disability/incapacity
- a congenital anomaly/birth defect

Other important medical events may also be considered an SAE when, based on appropriate medical judgment, they jeopardize the subject or require intervention to prevent one of the outcomes listed.

Adverse Reactions: Dapagliflozin

The most common adverse reactions associated with dapagliflozin (5% or greater incidence) were female genital mycotic infections, nasopharyngitis, and urinary tract infections. Other reported adverse reactions include:

- back pain
- nausea
- influenza
- dyslipidemia
- constipation
- discomfort with urination
- pain in the extremity
- male genital mycotic infections
- hypotension
- ketoacidosis
- acute kidney injury
- Urosepsis and Pyelonephritis
- Hypoglycemia with Concomitant Use with Insulin and Insulin Secretagogues
- Necrotizing Fasciitis of the Perineum (Fournier's Gangrene)

11.2.1 Serious Adverse Experience Reporting

Study sites will document all SAEs that occur (whether or not related to study drug) per [UCSF CHR Guidelines](#). The collection period for all SAEs will begin after informed consent is obtained and end after procedures for the final study visit have been completed.

In accordance with the standard operating procedures and policies of the local Institutional Review Board (IRB)/Independent Ethics Committee (IEC), the site investigator will report SAEs to the IRB/IEC.

12 DISCONTINUATION AND REPLACEMENT OF SUBJECTS

12.1 Early Discontinuation of Study Drug

A subject may be discontinued from study treatment at any time if the subject, the investigator, or the Sponsor feels that it is not in the subject's best interest to continue. The following is a list of possible reasons for study treatment discontinuation:

- Subject withdrawal of consent

SGLT2-02, [name]

- Subject is not compliant with study procedures
- Adverse event that in the opinion of the investigator would be in the best interest of the subject to discontinue study treatment
- Protocol violation requiring discontinuation of study treatment
- Lost to follow-up
- Sponsor request for early termination of study
- Positive pregnancy test (females)

If a subject is withdrawn from treatment due to an adverse event, the subject will be followed and treated by the Investigator until the abnormal parameter or symptom has resolved or stabilized.

All subjects who discontinue study treatment should come in for an early discontinuation visit as soon as possible and then should be encouraged to complete all remaining scheduled visits and procedures.

All subjects are free to withdraw from participation at any time, for any reason, specified or unspecified, and without prejudice.

Reasonable attempts will be made by the investigator to provide a reason for subject withdrawals. The reason for the subject's withdrawal from the study will be specified in the subject's source documents.

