CRITERIA	history of previous cystine kidney stones; and being able and willing to provide consent Exclusion Criteria: prior diagnosis of diabetes mellitus (type I or type II); current SGLT-2 inhibitor administration at the time of screening; SGLT-2 inhibitor administration within the last year prior to screening; vulnerable populations including incarceration status; anticipation of pregnancy during the study duration; unable to give informed consent; non-English primary language; pregnancy, lactation, or child- bearing age without birth control devices; and serious illness likely to cause death within the next 5 years.
TEST PRODUCT, DOSE, AND ROUTE OF ADMINISTRATION	Dapagliflozin 10 mg administered orally once daily for 4 weeks
CONTROL PRODUCT, DOSE AND ROUTE OF ADMINISTRATION	None
DURATION OF SUBJECT PARTICIPATION AND DURATION OF STUDY	Subjects will be on study for up to 6 weeks 
• Screening: 1 week to determine eligibility• Treatment: 4 weeks after the initial visit (Day 0)• Follow-up: 1 week after the last visit (Day 28)
CONCOMMITANT MEDICATIONS	Allowed: The participants will be allowed to continue any medications they are currently taking with the exception of those listed below under “prohibited”. Importantly, patients will be allowed to continue potassium citrate as this is an important mainstay of cystinuria treatment as discontinuation may lead to clinically significant cystine stone formation. Prohibited: Medications commonly used to treat diabetes, such as but not limited to insulin, metformin, and glipizides. These medications may interfere with the action of SGLT-2 inhibitors by altering the manner in which the body metabolizes and regulates glucose. Medications commonly used to treat cystinuria: thiola, penicillamine, alpha lipoic acid
EFFICACY EVALUATIONS	Efficacy in this study will be determined by utilizing mass spectrometry to analyze for the presence of sulfur in the urine before and after initiation of therapy with SGLT-2 inhibitor in our patients with cystinuria. Urinary cystine levels on 24-hour urine collection will also be measured.
PRIMARY ENDPOINT	Quantitative urinary sulfur via inductively coupled plasma optical emission spectroscopy (ICP-OES) in freshly voided urine

SGLT2-02, [name]

OTHER EVALUATIONS	

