7 CONCURRENT MEDICATIONS

All subjects should be maintained on the same medications throughout the entire study period, as medically feasible, with no introduction of new chronic therapies. However, patients will who are on medications commonly used to treat diabetes, such as but not limited to insulin, metformin, and glipizides will not be allowed to continue these while on study. These medications may interfere with the action of SGLT-2 inhibitors by altering the manner in which the body metabolizes and regulates glucose. Participants will also be asked to stop any medications commonly used to treat cystinuria they may be taking for the duration of the study as well: thiola, penicillamine, alpha lipoic acid.

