12.3 Withdrawal of Subjects from the Study

A subject may be withdrawn from the study at any time if the subject, the investigator, or the Sponsor feels that it is not in the subject's best interest to continue.

All subjects are free to withdraw from participation at any time, for any reason, specified or unspecified, and without prejudice.

Reasonable attempts will be made by the investigator to provide a reason for subject withdrawals. The reason for the subject's withdrawal from the study will be specified in the subject's source documents. As noted above, subjects who discontinue study treatment early (i.e., they withdraw prior to Visit 2) should have an early discontinuation visit.

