12.4 Replacement of Subjects

Subjects who withdraw from the study treatment will be replaced.

Subjects who withdraw from the study will be replaced.

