13 PROTOCOL VIOLATIONS

A protocol violation occurs when the subject or investigator fails to adhere to significant protocol requirements affecting the inclusion, exclusion, subject safety and primary endpoint criteria. Protocol violations for this study include, but are not limited to, the following:

- Failure to meet inclusion/exclusion criteria
- Use of a prohibited concomitant medication
- Failure to orally intake prescribed dosage on a daily basis

Failure to comply with Good Clinical Practice (GCP) guidelines will also result in a protocol violation. The Investigator will determine if a protocol violation will result in withdrawal of a subject.

When a protocol violation occurs, it will be discussed with the investigator and a Protocol Violation Form detailing the violation will be generated. This form will be signed by a Sponsor representative and the Investigator. A copy of the form will be filed in the site's regulatory binder and in the Sponsor's files.

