16.5 Investigator Responsibilities

By signing the Agreement of Investigator form, the Investigator agrees to:

1. Conduct the study in accordance with the protocol and only make changes after notifying the Sponsor (or designee), except when to protect the safety, rights or welfare of subjects.
2. Personally conduct or supervise the study (or investigation).
3. Ensure that the requirements relating to obtaining informed consent and IRB review and approval meet federal guidelines, as stated in § 21 CFR, parts 50 and 56.

SGLT2-02, [name]

4. Report to the Sponsor or designee any AEs that occur in the course of the study, in accordance with §21 CFR 312.64.
5. Ensure that all associates, colleagues and employees assisting in the conduct of the study are informed about their obligations in meeting the above commitments.
6. Maintain adequate and accurate records in accordance with §21 CFR 312.62 and to make those records available for inspection with the Sponsor (or designee).
7. Ensure that an IRB that complies with the requirements of §21 CFR part 56 will be responsible for initial and continuing review and approval of the clinical study.
8. Promptly report to the IRB and the Sponsor (or designee) all changes in the research activity and all unanticipated problems involving risks to subjects or others (to include amendments and IND safety reports).
9. Seek IRB approval before any changes are made in the research study, except when necessary to eliminate hazards to the patients/subjects.
10. Comply with all other requirements regarding the obligations of clinical investigators and all other pertinent requirements listed in § 21 CFR part 312.

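### The stop on cystinuria drugs is tied to the study rather than to dapagliflozin, so an early stopper who stays on is still asked to forgo thiol therapy, and that subject's off-drug Day 28 urine would count as the treatment sample

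*Combined protocol and SAP*

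**What the plan says.** **The ban.** Section 7 states: "Participants will also be asked to stop any medications commonly used to treat cystinuria they may be taking for the duration of the study". It names thiola, penicillamine and alpha lipoic acid. Section 7.1 repeats the request, and the synopsis lists the same drugs as prohibited without an end date. No section ties the ban to time on dapagliflozin or gives a restart rule.

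**Early stoppers.** Section 12.1 says that those who stop the drug early "should come in for an early discontinuation visit as soon as possible and then should be encouraged to complete all remaining scheduled visits and procedures". Section 12.3 refers back to this and says that "subjects who discontinue study treatment early (i.e., they withdraw prior to Visit 2) should have an early discontinuation visit". Section 12.4 adds: "Subjects who withdraw from the study treatment will be replaced". It applies the same rule to subjects who leave the study.

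**Violations and discretion.** Section 13 lists "Use of a prohibited concomitant medication" as a protocol violation, but also says: "The Investigator will determine if a protocol violation will result in withdrawal of a subject". Section 16.5 requires the investigator to follow the protocol and to notify the sponsor before making changes, "except when to protect the safety, rights or welfare of subjects".

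**Analysis.** Section 10.2 labels the Visit 2 (Day 28) urine as the treatment analysis. Section 14.3 compares it with baseline, and Section 14.1 analyses everyone enrolled. Appendix 1 has no column for an early discontinuation visit, and no section specifies a urine sample there.

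**The concern.** Section 1 counts thiol drugs among the mainstays that lower urinary cystine, so keeping them off is reasonable only while it serves the dapagliflozin measurement. Once dapagliflozin is permanently stopped, that reason goes. Section 1.1 says that the rise in urinary glucose approaches baseline about 3 days after the 10 mg dose is stopped, so a later Day 28 urine says little about treatment. As written, a prior thiol user who stops dapagliflozin but agrees to keep attending is still asked to go without thiol therapy.

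The second matter is separate and concerns any early stopper, thiol user or not. That subject's Day 28 urine enters the comparison as a treatment value with nothing to mark it as off drug. If a thiol drug has been restarted, its sulfur-containing mixed disulfides (Section 1) would also be counted, because the ICP-OES assay in Section 9.2.1 measures sulfur.

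**Working it through.** The plan gives no figure of its own on this point. The check sets the sections side by side and then does day-count and share arithmetic.

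**Inputs from the protocol**
- Treatment lasts 4 weeks, with 28 tablets and Visit 2 on Day 28 (Sections 4.1, 8.4.1, 8.4.2, 10.2). Section 8.1 says 1 week; I take the 4 weeks given elsewhere.
- Glucosuria approaches baseline at about 3 days (Section 1.1).
- Ten subjects are planned, those who stop treatment are replaced, and all enrolled are analysed (Sections 4.1, 12.4, 14.1).

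**Assumed, because the protocol gives no figure:** the stop day d and the number of early stoppers k who return on Day 28.

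**Step 1: does the ban outlast dapagliflozin?** It lasts as long as the subject is in the study (Sections 7 and 7.1). Section 12.1 keeps the early stopper in the study. Section 13 makes a restart a violation. Together these leave the request in force after the last dose. The parenthesis in Section 12.3 describes the same people as withdrawing, which blurs their study status, but it says nothing about medication.

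**Step 2: remaining restriction after stopping = 28 − d**
- d = 7: 28 − 7 = 21 days
- d = 14: 28 − 14 = 14 days
- d = 21: 28 − 21 = 7 days

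Counting the synopsis follow-up week as study time would move the end to Day 28 + 7 = 35 and add 7 days to each, giving 28, 21 and 14. Under either end point, the early stopper's total thiol break is no longer than a completer's.

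**Step 3: when is the Day 28 sample off drug?** The latest stop day that leaves about 3 days off drug is 28 − 3 = 25. Anyone who stops by Day 25 and returns gives a Day 28 urine taken after most of the glucosuria has gone.

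**Step 4: off-drug share of Day 28 values = k / (10 + k).** This assumes that each of the k stopped by Day 25, returns on Day 28 and is replaced by a subject who completes treatment.

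| k | share |
|---|---|
| 0 | 0/10 = 0% |
| 1 | 1/11 = 9.1% |
| 2 | 2/12 = 16.7% |
| 3 | 3/13 = 23.1% |

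How many of the k are prior thiol users cannot be derived from the protocol and may be zero.

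**The case against.** **The group may be empty.** Section 4.1 plans subjects on no current treatment except potassium citrate. The ban matters only for a prior thiol user who stops dapagliflozin early, stays, wants to restart and is held to the request. This stands as a limit on size. However, Sections 6.2 and 6.3 do not exclude thiol users, and Sections 7 and 7.1 provide for them.

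**The wording is soft.** Subjects are asked to stop and encouraged to stay, and they may leave freely. The investigator may withdraw them or depart from the protocol for their welfare, and the synopsis says that standard clinical care continues. All of this is true, so the ban is not an absolute bar. But these routes cost a violation form or the subject's follow-up, and one sentence would avoid both.

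**Readings that go too far.** A reader might infer that Sections 12.1 and 12.3 give opposing rules on the ban. They do not: neither mentions it, and Section 12.3 loosely restates Section 12.1 without forbidding later visits. A reader might also infer that the ban runs to Day 35. That is weak, because Section 10 and Appendix 1 schedule nothing after Visit 2, and SAE collection ends with the final visit (Section 11.2.1).

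**A thiol-free off-drug urine could be informative.** It could show whether sulfur returns toward baseline. The protocol plans no such comparison, but a restart before Day 28 would give it up. That is a real trade-off.

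**The analysis rule can wait for the SAP.** Section 14 promises one, and the reporting rule can sit there. A urine at the early discontinuation visit cannot be added after the fact. Dates of concomitant medication are already captured (Section 9.1.1), so thiol status needs no new data.

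**Conclusion.** The point holds as a cheap improvement to consider. Followed as written, the ban asks a prior thiol user who stops dapagliflozin on Day 7, 14 or 21 and stays on study to go 21, 14 or 7 more days to Day 28 without a mainstay therapy, for no planned study use. This rests on Section 12.1 governing study status and on at least one thiol user being enrolled, which is uncertain.

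Separately, off-drug Day 28 values would be pooled with treatment values: 9.1%, 16.7% or 23.1% of the total for one, two or three returning stoppers under the assumptions in Step 4. That part does not depend on thiol use.

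A reader might infer that an early stopper carries more stone risk than a completer. The documents do not support this. The thiol break is no longer, and the synopsis says that there are no published data on dapagliflozin's effectiveness for this indication, so no lost protection can be assumed. Sample size is unaffected.

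**What to change.** - **Sections 7 and 7.1:** state that the ban ends at permanent discontinuation of dapagliflozin. It ends after the early discontinuation urine if that is taken within about 3 days of the last dose, and otherwise at once. For completers it ends after the Day 28 sample.
- **Section 13:** exempt that restart from the violation list.
- **Section 12.1 and Appendix 1:** collect one freshly voided urine for sulfur at the early discontinuation visit.
- **SAP:** report early stoppers' Day 28 sulfur values as off dapagliflozin, with thiol status, apart from on-treatment values.
- **Section 12.3 (optional wording):** remove the parenthesis that equates stopping treatment with withdrawing.

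The cost is a few sentences and one urine assay per early stopper, with no extra visit. The downside is that a restart before Day 28 removes a clean thiol-free off-drug value, which the protocol does not plan to use.

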12.3 Withdrawal of Subjects from the Study

A subject may be withdrawn from the study at any time if the subject, the investigator, or the Sponsor feels that it is not in the subject's best interest to continue.

All subjects are free to withdraw from participation at any time, for any reason, specified or unspecified, and without prejudice.

Reasonable attempts will be made by the investigator to provide a reason for subject withdrawals. The reason for the subject's withdrawal from the study will be specified in the subject's source documents. As noted above, subjects who discontinue study treatment early (i.e., they withdraw prior to Visit 2) should have an early discontinuation visit.

12.4 Replacement of Subjects

Subjects who withdraw from the study treatment will be replaced.

Subjects who withdraw from the study will be replaced.

13 PROTOCOL VIOLATIONS

A protocol violation occurs when the subject or investigator fails to adhere to significant protocol requirements affecting the inclusion, exclusion, subject safety and primary endpoint criteria. Protocol violations for this study include, but are not limited to, the following:

- Failure to meet inclusion/exclusion criteria
- Use of a prohibited concomitant medication
- Failure to orally intake prescribed dosage on a daily basis

Failure to comply with Good Clinical Practice (GCP) guidelines will also result in a protocol violation. The Investigator will determine if a protocol violation will result in withdrawal of a subject.

When a protocol violation occurs, it will be discussed with the investigator and a Protocol Violation Form detailing the violation will be generated. This form will be signed by a Sponsor representative and the Investigator. A copy of the form will be filed in the site's regulatory binder and in the Sponsor's files.

14 STATISTICAL METHODS AND CONSIDERATIONS

Prior to the analysis of the final study data, a detailed Statistical Analysis Plan (SAP) will be written describing all analyses that will be performed. The SAP will contain any modifications to the analysis plan described below.

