4 STUDY DESIGN

4.1 Study Overview

This is a single center, proof of concept prospective cohort trial designed to assess the effect of daily oral administration of dapagliflozin 10 mg on cystine formation in freshly voided urine. Ten subjects are planned, each with previously diagnosed cystinuria and without current treatment except with potassium citrate medication.

SGLT2-02, [name]

Each subject will have an initial visit during which screening data will be reviewed to determine subject eligibility. Subjects who meet all inclusion criteria and none of the exclusion criteria will be entered into the study. Consent will be obtained as well as an initial examination and collection/analysis of freshly voided urine with mass spectrometry to serve as a baseline. The therapy under investigation, dapagliflozin 10 mg, will then be administered orally to each participant daily for four weeks, at which time each subject will return for a second visit for an analysis of freshly voided urine using mass spectrometry. The different urine collections will be compared and analyzed for differences with the prescribed therapy. No placebo will be used during this proof-of-concept study.

Total duration of subject participation will be up to six weeks. Total duration of the study is expected to be six weeks.

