5 CRITERIA FOR EVALUATION

5.1 Primary Efficacy Endpoint

The primary endpoint will be assessed via analysis using mass spectrometry of freshly voided urine and examining the resultant signals which signify the presence or absence of cystine as well as unbound cysteine amino acids and other reduction byproducts through the reaction with glucose. These will be assessed after 4 weeks of treatment with daily oral dapagliflozin 10 mg.

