8.2 Blinding

This is a nonblinded proof of concept study.

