14.1 Data Sets Analyzed

Data sets from all participants enrolled in the study will be analyzed. The primary efficacy endpoint will be assessed by medical history and physical exam, in addition to mass spectrometry data obtained at each study visit.

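### The primary endpoint is defined inconsistently and the SAP may be written as late as the final analysis, so the measure can be chosen after all paired results are known

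*Combined protocol and SAP*

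**What the plan says.** **Timing of the SAP.** Section 14 states: "Prior to the analysis of the final study data, a detailed Statistical Analysis Plan (SAP) will be written". It adds: "The SAP will contain any modifications to the analysis plan described below". No earlier milestone is given, and no part of the analysis is protected from modification.

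**Design.** Section 8.2: "This is a nonblinded proof of concept study". Section 4.1: "No placebo will be used during this proof-of-concept study". Section 10.1 (item 11) and Section 10.2 (item 6) have the urine analysed at Visit 1 and again at Visit 2.

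**Primary endpoint.** The descriptions differ by section:

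- Synopsis, Primary Endpoint: "Quantitative urinary sulfur via inductively coupled plasma optical emission spectroscopy (ICP-OES) in freshly voided urine". The objective (synopsis and Section 3.1) and the synopsis analysis plan also centre on sulfur, but name mass spectrometry as the method. Section 9.2.1 collects urine for sulfur by ICP-OES.
- Section 5.1: mass spectrometry, "examining the resultant signals which signify the presence or absence of cystine as well as unbound cysteine amino acids", together with other products of the reaction with glucose. Sulfur is not mentioned.
- Section 14.1: "The primary efficacy endpoint will be assessed by medical history and physical exam, in addition to mass spectrometry data obtained at each study visit".
- Section 14.3: a quantitative comparison of the two mass spectrometry analyses, with no variable, scale, summary or test. The synopsis has the comparison as both qualitative and quantitative.

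The synopsis also lists 24-hour urinary cystine under efficacy, with no rank.

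**The concern.** In a before/after study without a control arm, a participant's paired difference is that person's apparent treatment effect. Nothing has to be unblinded to see it. A plan written once those differences are available can settle on whichever definition moved in the hoped-for direction and still comply with Section 14.

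The definitions could disagree. Total sulfur does not separate cystine from cysteine, whereas the Section 5.1 signals are meant to. A treatment that split cystine into cysteine could change the second and leave the first where it was.

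Section 14.5 and the synopsis make further research depend on promising results, and no criterion for promising is given. A reader of the report could not tell whether the measure shown was fixed in advance or selected.

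**Working it through.** **1. Can results be known before the SAP is due?** Section 14 sets the deadline at the final analysis. Section 10 produces the urine analyses at each visit. Section 8.2 removes blinding, and the documents describe no restriction on access to the results. All ten paired results can therefore be in hand before the deadline.

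**2. How many candidate measures are there?**

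| Source | Measure | Usable as a before/after change? |
|---|---|---|
| Synopsis, Sections 3.1 and 9.2.1 | Sulfur, quantitative | Yes |
| Section 5.1 | Cystine, cysteine and byproduct signals | Yes if quantified; described partly as present or absent |
| Section 14.1 | History and examination, plus mass spectrometry | History and examination: no |

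History is recorded at Visit 1 only (Section 9.1.3, Section 10.1, Appendix 1). The examination is complete at Visit 1 and abbreviated at Visit 2, and no variable is derived from it. Two is thus the count best supported as paired measures. A third arises if the cystine and cysteine signals are taken separately, or if the unranked 24-hour cystine is brought in.

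**3. Size.** The plan has no alpha, test, effect size or SD, so it has no figure of its own to reproduce. Assumptions for illustration: two-sided alpha 0.05 per measure, one paired t test per measure, n = 10 (the planned number), no true effect on any measure, and the study called positive if any measure is significant.

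For k independent measures, the probability of at least one false positive is 1 − (1 − 0.05)^k:

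- k = 1: 5%
- k = 2: 1 − 0.95² = 1 − 0.9025 = 0.0975
- k = 3: 1 − 0.95³ = 1 − 0.8574 = 0.1426

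For correlated measures, 40,000 simulated studies of ten normally distributed paired differences, with equal correlation between measures, gave:

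| Correlation | Best of 2 | Best of 3 |
|---|---|---|
| 0 (formula) | 9.8% | 14.3% |
| 0.5 | 9.3% | 12.8% |
| 0.8 | 7.9% | 10.3% |

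The documents give no correlation between the measures, hence the range. With one measure and one test fixed beforehand, the rate returns to the assumed 5%.

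**The case against.** **Sulfur is the dominant definition.** It is the objective in the synopsis and Section 3.1, the endpoint in the synopsis, the focus of the synopsis analysis plan and an assay in Section 9.2.1. This stands: a reader might infer three primary endpoints of equal standing, and the documents do not support that. But Section 5.1, which carries the primary endpoint heading, omits sulfur, Section 14.3 names no variable, and no rule says which section prevails.

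**Protocol changes need ethics approval.** Sections 16.1, 16.2 and 16.5 require it, and Section 14 has modifications written into the SAP, so a departure should leave a record. This is partial protection. Choosing among definitions already in the protocol is not clearly an amendment.

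**It is a ten-patient proof of concept with no planned test.** This also stands, and it makes the error rates illustrative. Selection still distorts the direction and size of the effect reported, test or no test.

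**Stronger readings to avoid.** A reader might take the interim analysis as a planned look at efficacy; the synopsis and Section 14.4 say it is for safety, and the point does not rest on it. A reader might also multiply the candidates by raw and normalised scales; no section mentions normalisation, so such a count has no basis in the documents. Nor do the documents suggest any intent to select.

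**Conclusion.** The point holds as a gap in prespecification. The primary endpoint is inconsistently defined, with sulfur dominant, and the Section 14 timing rule allows the definition to be settled after all paired results are known.

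Under the assumed two-sided 5% level, the illustrative cost is a false-positive rate of about 8–10% for a choice between two measures and about 10–14% for three, against 5% for one. The ranges run from correlation 0.8 to 0. They rest on paired t tests that the protocol does not plan, and should not be read as operating characteristics of this study.

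The conclusion also assumes that no separate dated SAP already fixes the measure; none is among the documents reviewed. Further research is only to be considered if results are promising (Section 14.5), so the choice would influence that decision without being its sole determinant.

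**What to change.** 1. **Section 14:** require the SAP to be finalised and dated before the first Visit 2 urine is assayed, with any later change labelled post hoc.
2. **One primary measure:** name it, with its scale and paired summary (for example, the mean or median within-person change with a confidence interval). The documents' dominant definition is quantitative sulfur in freshly voided urine by ICP-OES. Use identical wording in the synopsis and Sections 3.1, 5.1, 14.1 and 14.3.
3. **Assay name:** align it in Section 9.2, Section 10 and Appendix 1, which now differ between ICP-OES and mass spectrometry.
4. **Section 14.1:** delete medical history and physical examination from the efficacy endpoint.
5. **Remaining measures:** rank the cystine and cysteine signals and 24-hour cystine as exploratory.

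The cost is wording and a short SAP written earlier. It needs no extra participants, visits or assays. The downside is less freedom to choose the measure later.
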